5.4.3 Study Design

This study is a multinational, multi-center, randomized, double-blind, placebo-controlled efficacy and safety study. This study aims to assess the efficacy of a single administration of 8 mg, 16 mg, or 32 mg moxidectin per oral in achieving Complete Cure at Day 28. This study also aims to assess the safety of three strengths of single moxidectin doses in patients aged 18 years and older with scabies.

Scabies occurs in all regions and populations around the world. As the number of subjects required for this protocol precludes recruitment in a single reference site and it is important to evaluate the overall treatment effect based on subjects in all regions, centers in multiple countries are planned. It is planned that centers from the US and Latin America will be included and that no center, country, or regional quotas will be imposed. The prevalence of scabies in the

US is generally considered to be low with higher prevalence observed in settings or countries with socio-economically disadvantaged or vulnerable populations, while Latin American countries are generally considered to have higher disease prevalence⁵. Unless otherwise specified, data will be pooled across regions. There is no data to suggest that the course or severity of disease differs between populations in the US and Latin American target regions, nor that there are any clinically relevant differences in intrinsic and extrinsic factors that would result in clinically meaningful differences in efficacy.

The moxidectin doses proposed for evaluation in this study are within the range of doses previously studied and no subject will receive more than a single oral dose of moxidectin. Only subjects aged 18 years and older will participate in this study as there are limited data on the pediatric use of moxidectin, which has only been administered to subjects ≥ 4 years with, or at risk of onchocerciasis, at an 8 mg single dose per oral. Only one subject will be enrolled per household; where more than one household member is screened for participation in the study, the enrolled (index) subject will be the youngest eligible member of the household.

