1.2 Changes to Protocol Planned Analyses

The following changes have been made to the planned analyses described in the clinical study protocol MDGH-MOX-2002 Version 3 dated 28 Dec 2023:

- The description of the process for randomization, described under Section 10.1 of the current study protocol, was updated in this SAP Section 5.1. Instead of a unique screening number, a site specific sequential Subject Number was allocated to each subject who provided written informed consent. This Subject Number was used throughout the study to identify the subject. A unique Randomization Number was assigned to the subject upon randomization and this randomization number was only recorded on the Randomization electronic case report form (eCRF) page. Study drug was dispensed according to the Randomization Number, not according to the Subject Number.
- Two additional sensitivity analyses have been included to support the primary efficacy analysis:
 - A Completers Analysis excluding subjects with missing data for the primary endpoint with the exception of subjects exposed to scabicides.
 - An analysis that adjusts for Baseline lesion count as the sole covariate, other than randomized treatment group.
- The protocol states that sensitivity analyses will be conducted to assess the impact of missing data on the results. As such, a tipping point analysis has been included in the SAP.
- A repeat of the primary analysis within each Region will not be conducted due to anticipated small sample size within one of the Regions. However, descriptive analyses of the primary efficacy endpoint stratified by Region will be provided.

- Exploratory pairwise comparisons between each of the moxidectin dose groups have been added.
- For the non-informative missing data, the Complete Cure endpoint may be imputed via a fixed value using the methodology detailed in [Appendix 1](#). Should the missing data due to non-informative reasons be 5% of the total sample size, (approximately 200 subjects), a multiple imputation (MI) approach will be implemented using the methodology detailed in [Appendix 2](#).
- The following additional exploratory endpoints have been included in this SAP that are not otherwise listed in the current study protocol:
 - The Day 28 Complete Cure without regards to pruritus.
 - The proportion of index subjects achieving clearance for each individual component of the Complete Cure endpoint

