9 STATISTICAL METHODS OF ANALYSIS

9.1 General Analytic and Reporting Principles

The results of the statistical analyses will be reported using summary tables and figures, with all data reported as listings. All analyses will be performed using SAS Version 9.4 or later.

Data will be summarized in tabular form by dose group in order of ascending dose (moxidectin 8 mg, moxidectin 16 mg, moxidectin 32 mg), placebo and overall subjects.

Summary statistics for continuous variables will consist of the number of non-missing observations (n), mean, standard deviation (SD), minimum, median and maximum, unless specified otherwise. Summary statistics for categorical variables will include the number (count) and percentage of subjects. In general, the percents will be calculated using the denominators for each treatment group within the analysis population being considered. Percentages based on other denominators will be noted. If relevant, tabulations of categorical data will include all categories captured on the eCRF even if no observations in the database appear in those categories. In this situation a '0' will be inserted. For certain categorical variables the number of participants with missing data may also be provided; however, the number missing will not be included in the calculations of percentages.

For proportions, asymptotic Wald confidence intervals (CIs) will be calculated. When the normal approximation may not hold, exact CIs may also be calculated. Confidence intervals based on bootstrapped standard errors (SEs) will be flagged in tables if relevant.

No preliminary rounding will be performed. Any rounding will only occur after analysis for the purposes of data presentation.

For any analyses using a randomized component such as bootstrapped statistics or permutation tests, the randomization seeds used to produce the analysis will be saved and documented to enable the results to be reproducible.

9.1.1 Final Efficacy Analysis at Day 42

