As supportive analyses, the Day 28 Complete Cure rates for each moxidectin group and placebo, as well as the risk difference and 95% CIs for each pairwise comparison, will be calculated within each region. For these region subgroup analyses the proportion of index subjects achieving a Day 28 Complete cure for each randomized treatment group within region will be the unadjusted proportions with Wald 95% CIs for a single proportion. The 95% CI for the risk difference will be the Wald CIs for the difference between two independent proportions using the unpooled variance. Any significance test of the risk difference conducted within region will

be viewed as supportive and exploratory due to the potential lack of power. The 95% CIs and any hypothesis tests for these supportive analyses will not be adjusted for multiplicity.

See [Appendix 3](#) for specification of the logistic model and bootstrapping.

9.11.2 Handling of Missing Data for the Primary Analysis of Day 28 Complete Cure

For the Day 28 Complete Cure endpoint, subjects exposed to rescue medication (scabicides, including permethrin, ivermectin, benzyl benzoate, sulfur, lindane, crotamiton, malathion, tea tree oil, or spinosad) prior to the Day 28 assessment will be imputed as a non-responder. If a subject is exposed to a scabicide as a concomitant medication with an unknown start date, they will also be imputed as a non-responder unless the end date is known and is after Day 28. Additionally, subjects with missing Day 28 Complete Cure assessments due to missed visits or incomplete scabies assessments at Day 28 will also be imputed as non-responders. An exception would be if the missing Complete Cure endpoint was missing for reasons deemed as non-informative i.e. the Day 28 visit was missed because weather conditions prevented travel. For the non-informative missing data, the Complete Cure endpoint may be imputed via a fixed value using the methodology detailed in [Appendix 1](#). Should the missing data due to non-informative reasons be greater than 5% of the total sample size (approximately 200 subjects), a multiple imputation approach will be implemented, see [Appendix 2](#).

The determination of the use of rescue medication as well as informative vs non-informative missing data will be conducted prior to the blind break for the Day 42 analysis, see Section [9.6](#).

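### Within-region cure rates and risk differences get Wald intervals although the SAP expects one region to be small; the only fallback is optional and has no trigger

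*SAP*

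**What the plan says.** For the supportive analyses by region, SAP 9.11.1 specifies "unadjusted proportions with Wald 95% CIs for a single proportion" for each arm's cure rate and "Wald CIs for the difference between two independent proportions using the unpooled variance" for each comparison with placebo. It adds: "The 95% CIs and any hypothesis tests for these supportive analyses will not be adjusted for multiplicity". The multiplier is therefore 1.96.

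SAP 1.2 drops the repeat of the primary analysis by region "due to anticipated small sample size within one of the Regions", but keeps descriptive results by region. Protocol 5.4.3 says that "no center, country, or regional quotas will be imposed", so nothing fixes how many subjects each region contributes. Randomization is 1:1:1:1 within region (SAP 5.1), so a small region is split four ways.

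The general rule in SAP 9.1 is: "For proportions, asymptotic Wald confidence intervals (CIs) will be calculated". It continues: "When the normal approximation may not hold, exact CIs may also be calculated". SAP 9.11.5.1 asks for 95% intervals on the exploratory cure rates by arm, overall and again by region, without naming a type, so the 9.1 default applies there.

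**The concern.** The Wald interval relies on a large-sample approximation and takes its width from the observed proportion. With few subjects its true coverage can fall well below 95%. When everyone or no one in a cell is cured, the estimated variance is zero and the interval is a single point. The SAP foresees sparse data in one region and adapts the primary analysis to it, yet names a large-sample interval for that same region.

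At stake is how readers judge regional consistency and the exploratory cure rates by dose. An arm with 5 of 5 cured would be printed as 100% with limits of 100% and 100%, which suggests certainty from five people.

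**Working it through.** **The plan's own figure first.** SAP section 4 and Protocol 15.2.1 state about 75% power for 50 per arm, 40% against 70%, pooled Z-test, two-tailed alpha 0.019 (z = 2.3455).
- Null SE = √(2 × 0.55 × 0.45 / 50) = 0.0995.
- Alternative SE = √(0.4 × 0.6/50 + 0.7 × 0.3/50) = 0.0949.
- Power = Φ((0.30 − 2.3455 × 0.0995)/0.0949) = Φ(0.70) = 0.759, which agrees.
- The large-sample Dunnett critical value for three comparisons is 2.349, or alpha 0.0188, which rounds to 0.019.

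**Inputs.** The rates of 40% (placebo) and 70% (moxidectin) come from the sample-size sections. The interval formulas come from SAP 9.11.1. The per-arm n within the small region is not in the documents; 3 to 20 is an assumed range.

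**Formulas.**
- Wald interval, one proportion: x/n ± 1.96 √(p̂(1 − p̂)/n).
- Exact coverage: the sum of the binomial probabilities of all x whose interval contains the true p. For a risk difference, the sum runs over all pairs of counts.
- Probability of zero width: pⁿ + (1 − p)ⁿ.

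**One cell by hand, n = 5, p = 0.70.**
- x = 0 and x = 5 give zero width and miss: 0.3⁵ + 0.7⁵ = 0.0024 + 0.1681 = 0.1705.
- x = 1 gives 0.20 ± 0.351, upper limit 0.551, and misses: probability 5 × 0.7 × 0.3⁴ = 0.0284.
- All other x cover. Coverage = 1 − 0.1705 − 0.0284 = 0.801.

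**Results at the design rates (%).** The first three result columns are for a single true rate of 40% / 70%; the last two are for the risk difference between them.

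| n per arm | Wald coverage | Wald zero width | Wilson coverage | Wald, difference | Newcombe, difference |
|---|---|---|---|---|---|
| 3 | 72.0 / 63.0 | 28 / 37 | 93.6 / 97.3 | 83.7 | 93.9 |
| 5 | 83.5 / 80.1 | 8.8 / 17.0 | 99.0 / 96.9 | 88.4 | 95.7 |
| 8 | 84.4 / 93.1 | 1.7 / 5.8 | 93.3 / 94.2 | 93.1 | 95.2 |
| 10 | 89.9 / 84.0 | 0.6 / 2.8 | 98.2 / 92.4 | 93.4 | 93.6 |
| 15 | 93.9 / 94.9 | 0.0 / 0.5 | 93.9 / 91.5 | 91.3 | 94.6 |
| 20 | 92.8 / 94.7 | 0.0 / 0.1 | 96.3 / 97.5 | 94.3 | 94.7 |

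With placebo at 40% and all three doses at 70%, the chance that at least one of the four regional intervals has zero width is 1 − (1 − 0.28)(1 − 0.37)³ = 82% at n = 3. The same formula gives 48% at n = 5 and 18% at n = 8.

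**More extreme rates.** For 20% against 90%, Wald coverage of the difference is 79.4% (n = 5), 81.4% (n = 10) and 94.1% (n = 20).

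**All cured.** Wald gives 100% to 100% at any n. The Wilson lower limit is n/(n + 1.96²): 5/8.84 = 56.6% for 5/5 and 72.2% for 10/10. The Clopper-Pearson lower limit is 0.025^(1/n): 47.8% and 69.2%.

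**Full arms, n = 50.** Wald coverage and zero-width probability are 87.9% and 0.5% at a true rate of 90%, 92.0% and 7.7% at 95%, and 63.5% and 36.4% at 98%. A result of 49/50 has a Wald upper limit of 101.9%.

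**The case against.** The SAP already recognises the problem: section 9.1 allows exact intervals when the normal approximation is doubtful, and using them needs no amendment. That softens the point but does not remove it. The provision is permissive, states no trigger, names no method, does not say how it applies to risk differences, and leaves the Wald interval in the table. The text in 9.11.1 is also the more specific.

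The size rests on an assumed n. This stands. A reader might infer that every regional interval will be badly wrong; the documents do not support that. At the design rates the Wald risk difference covers 93.1% from 8 per arm, dipping to 91.3% at 15, and improves little with Newcombe at most of these sizes.

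A reader might also infer that microscopic or dermatoscopic cure will be near 100%, so that even full arms are affected. No expected rate for it is given. The nearest data (Protocol 5.3.2.2.3) are 100% mite mortality by confocal microscopy, with 4 to 8 subjects at the doses concerned, which is a different endpoint. Here cure also requires no burrows, and scabicide users count as not cured (SAP 6.3). The separate mite, egg and scybala proportions are not in the 9.11.5.1 list that receives intervals.

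Nor is Wilson perfect: it covers 85.7% at n = 3 with a true rate of 95%, though Wald covers 13.5% there. At n = 15 and 70% Wilson covers 91.5% against 94.9% for Wald.

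Finally, no decision hangs on these intervals, and a reader who sees the denominators can discount a zero-width one. That limits the importance of the point but does not make the printed limits valid.

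**Conclusion.** The point holds in a limited form. The SAP names Wald intervals where it expects few subjects, and its only safeguard is discretionary. If the small region has about 5 or fewer per arm, coverage at the design rates is roughly 63% to 84% for single rates and 84% to 88% for the difference, and a zero-width interval somewhere among the four arms is likely or nearly an even chance. From 8 to 10 per arm, single-rate coverage is uneven (84% to 93%), while the difference is close to nominal at the design rates, though not at more extreme ones. In full arms of 50, serious failure needs a true rate of about 98% or above.

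All of this depends on a regional n that the documents do not give. The affected outputs are supportive or exploratory. It would be wrong to conclude that the primary result is at risk: the primary test, its bootstrapped interval and the stated power do not use these within-region intervals.

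**What to change.** In SAP 9.1, the within-region part of 9.11.1, and 9.11.5.1, replace Wald as the reported interval:
- for single proportions, name Wilson, or Clopper-Pearson if guaranteed coverage is preferred to narrower limits;
- for unadjusted risk differences, name Newcombe or Miettinen-Nurminen.

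State that the primary bootstrapped interval is unchanged. Make the change before the Day 42 unblinding, since SAP 1.1 labels anything not defined in advance as post hoc.

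The cost is a wording change and standard software options. The intervals become asymmetric, and in all-or-none cells much wider: 5/5 goes from zero width to about 57% to 100% with Wilson. That width is what five subjects can support.

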9.11.3 Sensitivity Analyses for Primary Analysis of Day 28 Complete Cure

9.11.3.1 PPAS and Complete Data Analyses

Sensitivity analyses for the above primary efficacy analysis will be conducted using the same methodology outlined above for the primary efficacy analysis. The first sensitivity analysis will repeat the primary efficacy analysis using the PPAS. The second sensitivity analysis will repeat the primary efficacy analysis for the Complete Analysis Set.

9.11.3.2 Tipping Point Analysis

A tipping point (TP) analysis will be conducted to determine the sensitivity of the primary efficacy result, if positive, to various patterns of outcomes in subjects with missing Day 28 Complete Cure endpoints. Initially, the first TP iteration will be to make a worst-case assumption that all subjects imputed as non-responders in the placebo group for the primary analysis are now imputed as responders for the first TP iteration. Conversely, all subjects in each of the moxidectin groups who were imputed as non-responders in the primary analysis remain non-responders in the first TP iteration. If the pairwise comparisons that were significant for the primary analysis continue to be statistically significant for this first “worst case” iteration, it may be assumed that an analysis using the true, but unknown, missing data would also be statistically significant.

If the “worst case” iteration fails to reject the null hypothesis for a pairwise comparison that was significant in the primary analysis, then the TP analysis will continue to determine how much the non-significant “worst case” iteration will need to be “relaxed” to achieve statistical significance. That is, one-by-one the imputed non-responders in the placebo group who were switched to a responder in the “worst case” iteration, will be switched back to their original non-responder status while the imputed non-responders in the moxidectin groups continue to be non-responders for all further TP iterations.

For example, if there were 8 imputed non-responders in the placebo group for the primary analysis, all 8 will simultaneously be considered responders for the worst-case iteration. If the worst-case iteration is non-significant, then the next TP iteration will switch one of the 8 participants back to a non-responder, re-run the primary analysis and calculate the adjusted p-value for each pairwise comparison of moxidectin to placebo. If this TP iteration is still non-significant a third TP iteration will be run where a second subject among the 8 is switched back to their original non-responder status – a total of 2 of 8 such subjects for the third TP iteration. At the 8th iteration, all the 8 subjects in the placebo group who were imputed non-responders will have been switched back to their original non-responder status. Since the imputed non-responders in the moxidectin groups remain non-responders regardless of iteration, in this hypothetical example, the 8th iteration would reflect an analysis where all imputed non-responders remain non-responders which is essentially the primary analysis.

The iteration prior to the first statistically significant result favoring moxidectin will be considered the TP for that particular pairwise comparison. It is recognized that this process does not examine all possible combinations of success/failure outcome iterations for all treatment groups; however, a TP analysis that sequentially iterates outcomes away from the worst case toward the outcomes imputed for the primary analysis should provide insight as to how robust the primary results are to missing data.

Since the primary analysis uses a method that produces a marginal risk difference in proportions adjusting for region, it is noted that region may differ among subjects in the original imputed non-responder subgroup. Hence, for each successive TP iteration following the worst-case analysis described above, the subject in the randomized placebo group, whose outcome will change from success to failure and be added to the cumulative number of subgroup subjects who already switched at previous TP iterations, will be randomly selected from the non-responder subgroup pool who have not yet been randomly selected from the placebo group at previous iterations.

For this TP sensitivity analysis, the analytic method used for the primary analysis will be repeated. If the primary analysis could not be adjusted for region due to small sample sizes in some stratified treatment groups, then the TP sensitivity analysis will not adjust for region either. Also, only those moxidectin dose groups that were statistically significant to placebo in the primary analysis will be included in the TP sensitivity analysis.

The imputed success/failure outcome used in the primary analysis will remain unchanged throughout the TP analyses for subjects whose outcome was missing due to non-informative reasons

9.11.4 Exploratory Analyses of the Primary Endpoint

9.11.4.1 Pairwise Comparisons Between the Three Moxidectin Dose Groups

An exploratory analysis comparing each of the 3 moxidectin dose groups to each other with respect to Complete Cure will also be conducted. These pairwise comparisons will be conducted using the same analysis used for the primary analysis as described in Appendix 3. For these pairwise comparisons, no p-values will be calculated, only the 95% CIs for the pairwise Risk Differences will be provided. Additionally, unlike the pairwise comparisons conducted for the primary analysis, the 95% CIs for these exploratory pairwise comparisons will not be adjusted for multiplicity.

9.11.4.2 Adjustment for Baseline Lesion Count

An additional exploratory sensitivity analysis will assess the risk difference between each moxidectin dose group versus placebo after adjusting for Baseline lesion count. The analysis will use the same methodology for the primary analysis with appropriate imputations, but the logistic model will include randomized treatment group and Baseline lesion count. Region will be excluded from the model to keep the number of covariates small relative to the FAS sample size. Baseline lesion count will be categorized into three groups. The three baseline lesion groups are:

- Subjects with ≤ 10 lesions
- Subjects with 11 to 49 lesions
- Subjects with ≥ 50 lesions

In the model, dummy variables will be created for the lesion count categories using the subjects with ≤ 10 lesions category as the reference group. Each of the individual group proportion of FAS subjects achieving Day 28 Complete Cure and the three pairwise risk differences of each moxidectin group compared to placebo will be presented adjusting for Baseline lesion count. The 95% CIs will be displayed for each of the adjusted point estimates. The p-values for the risk differences will also be provided. This analysis will not be adjusted for multiplicity.

An additional sensitivity analysis will include the continuous metric for Baseline lesion count as a covariate after taking the natural log for each subject's Baseline count. The logistic model will then only include randomized treatment group and the logged Baseline lesion counts. The point estimates, CIs, and p-values described above will be presented adjusting for the continuous log transformed Baseline lesion count. Additional *ad hoc* analyses may be conducted to further explore the relationship between Baseline lesion count and Complete Cure.

